Experimental Approach. We have already collected and biobanked fecal and blood samples from 40 well-characterized (including 20 newly diagnosed, treatment naïve) PD patients and 20 matched [for age, gender, race, BMI] healthy controls (HC). We also have comprehensive dietary information (using 24 hour diet recall questionnaire prior to stool collection) in these subjects. To profile the human fecal microbiome, DNA will be extracted using the NexteraXT sample preparation kit adapted for acoustic liquid handling, and subjected to whole-genome shotgun metagenomic sequencing. This procedure is routine to our team [87-90], but briefly, shotgun metagenomics will be performed using the NexteraXT barcoded kit on the Labcyte Echo and TPP Mosquito platforms, allowing low-biomass inputs. Sequencing will be performed at 2X150 bp using the Illumina HiSeq 4000 platform, allowing excellent depth of coverage, and mapped to ~47,000 reference bacterial genome sequences using HUMAnN2. In our experience, assembly using metaSPADES [91] does not work well for data generated using this method, but when the reference genome collection is fairly complete, as it is for human stool microbiomes, read mapping provides excellent taxonomic and functional results. Bioinformatics analyses using HUMAnN2 and QIIME [92] will map metagenomic DNA data sets to determine gene content and the corresponding microbial pathways involved. Though we will mine this data exhaustively for global multi-parameter analysis, we will specifically determine whether genes associated with known SCFA pathways are enriched or depleted differentially in PD patients and controls.

Our hypothesis is that microbiota-derived metabolites contribute to PD symptoms, and may be protective or pathogenic depending on metabolite levels and/or ratios. The question is whether hallmark changes in microbiome composition and function are specific to PD or are the consequence of aggregated α Syn in the ENS and intestinal dysfunction. To answer this question, we will collect stool samples from patients with Multiple System Atrophy (MSA), a synucleinopathy, and α -synuclein-dementia [n=20 each group], and interrogate their microbiome composition and function using shotgun metagenomics as described. Comparison to the PD microbiome will address specificity to related neurodegenerative disease, and this knowledge could also further expand the role of microbiome to additional disorders where α Syn plays a pathogenic role.

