Each household and first-degree relative study subject will be evaluated to ensure there is no clinical evidence of neurological disorders including PD. Also, these subjects will complete a 24 hour diet recall questionnaire before stool collection and validated 3 month food frequency questionnaires to collect dietary information similar to PD patients. Each subject (including PD subjects) will complete a smell questionnaire and a sleep questionnaire to determine whether these “control” subjects have loss of smell or have REM sleep disorders because these

conditions increase the risk of PD. For assessing smell, we will use the UPSIT questionnaire [94, 95]. For assessing REM sleep disorder, we will use RBD1Q which consists of a single question, answered “yes” or “no,” as follows: “Have you ever been told, or suspected yourself, that you seem to ‘act out your dreams’ while asleep (for example, punching, flailing your arms in the air, making running movements, etc.)?” [96] We predict that at least 20 PD patients/MSA will have both household spouse and first degree relative willing to provide stool samples for this study.

Second, in the longitudinal study, we will collect stool every 3 months (with 3 day diet questionnaire prior to each collection) over 12 months and determine microbiome composition over time. All PD subjects will undergo clinical assessments at baseline and end of the study to determine the severity of PD. These assessments will include: Movement Disorder Society-Sponsored Revision of the Unified Parkinson’s Disease Rating Scale (MDS-UPDRS); Hoehn and Yahr Stage (HY); Non-Motor symptoms Scale (NMSS); Montreal Cognitive Assessment (MoCA). We will correlate the microbiome data with PD symptoms, diet and response to treatment and progression of disease. These studies will determine whether disease progression and factors such as PD medications and diet significantly impact microbiome composition. Further, we will determine whether changes in SCFA-producing bacteria (as part of Aim 1.1) and/or abnormal SCFA profiles (as part of Aim 1.3) correlate with severity of PD symptoms.

Inclusion/ Exclusion Criteria:

For Parkinson’s disease subjects:

Inclusion criteria:

1. 40-80 years of age
2. Documented diagnosis of Parkinson’s disease
 - For cross sectional study- the Parkinson’s disease stages 1-4 are eligible
 - For longitudinal study- the Parkinson’s disease stages 1-2.5 are eligible

Exclusion criteria:

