Statistical analysis. Group descriptive statistics will be performed on all variables. Normality of distribution will be assessed by the Lilliefors test, and homogeneity of variance will be examined with the Levene test. Inter-group differences will be analyzed by one or two-way ANOVA using the Holm-Sidak test for comparison. For animal research, based on our previous studies over many years, 6-8 mice per group will be needed (and all studies performed in duplicate) on average in each group to achieve a probability of 88% that the study will detect a relationship between independent and dependent variables at a two-sided 5% significance level. This power calculation assumes that the true change in the dependent variables is 0.53 standard deviations per one standard deviation change in the independent variable. For human subjects work, based on the humanized mouse data in **Figure 4** and our publication [30], a sample size of 20 human donors per group achieves 96% power to detect a small effect size ($f^2 = 0.08$) attributed by patient category by an F-test with an $\alpha = 0.05$, when adjusting for 7 additional explanatory variables.

Overall Strategic Plan. De-identified stool samples collected at RUMC will be sent to Caltech for colonization of mice, as we have been doing for over 2 years. Additional samples for ongoing enrollment will be collected at RUMC and UW. Fecal swabs from all samples will be sent to UCSD for microbiome profiling (metagenomics). All samples will be coded so that investigators at Rush and UW can link it back to the subjects. Investigators from UCSD, Caltech and Purdue will not have access to the link to the codes with subject identifiers. Fibers will be developed and optimized in bioreactors at Purdue. Fecal samples and dietary fibers will be sent to Caltech, where all mouse treatments will take place. Fecal samples from Rush will also be sent to the [name] lab at Purdue to perform *in vitro* fermentation tests. The [name] laboratory will administer the motor tests, assess neuroinflammation, and measure α Syn aggregation; while the [name] laboratory will perform the CLARITY analysis and neuronal activity tests. Finally, fecal samples from mice will be sent to UCSD for metagenomics, and to Purdue for *in vitro* fermentation and SCFA analysis. We predict that specific, molecular interactions

Formatted: Font: Italic

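### The human power statement (20 donors per group, f² = 0.08, 96% power) does not follow from its own inputs: 20 versus 20 gives about 41%, and no grouping of 20 per category that the protocol describes reaches 96%

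*Protocol*

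**What the plan says.** The Statistical analysis section of the protocol gives one power calculation for the human work: "a sample size of 20 human donors per group achieves 96% power to detect a small effect size". It sets the effect at f² = 0.08, "attributed by patient category by an F-test with an" alpha of 0.05, "when adjusting for 7 additional explanatory variables". The number of patient categories, the numerator degrees of freedom and the total N are not given.

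The group sizes have to be taken from Specific aim 1:

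- Aim 1.1, Experimental Approach: 40 biobanked PD patients and 20 controls ("including 20 newly diagnosed, treatment naïve) PD patients and 20 matched [for age, gender, race, BMI] healthy controls (HC").
- Aim 1.1, same section: MSA and α-synuclein dementia, "n=20 each group".
- Aim 1.2, Experimental Approach: an expectation that "at least 20 PD patients/MSA will have both household spouse and first degree relative willing to provide stool samples for this study".

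**The concern.** The sentence supplies almost everything needed to check it, and 96% is far too high for the rest. In a two-group comparison f² = 0.08 is a standardised difference of 2 × √0.08 = 0.57, and 20 per group cannot detect that with near certainty.

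This is the only power calculation the protocol gives for the human comparisons: PD against HC, and PD against the other synucleinopathies. Aim 1.1 uses the second to judge whether dysbiosis is specific to PD, so a non-significant difference there could be read as evidence that it is not. Aim 4.2 chooses candidate bacteria by their significant depletion in this cohort. In both places a null result would look much more trustworthy with 96% power behind it than the sample size allows.

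**Working it through.** **Inputs.** From the Statistical analysis section: 20 per group, f² = 0.08, alpha 0.05, F-test on patient category, 7 further explanatory variables, stated power 96%. From Aims 1.1 and 1.2: the cohort sizes above. The number of categories is not given, so it is varied.

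**Method.** Test of the increment due to category in a linear model, with:

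- numerator df u = categories − 1
- error df v = N − u − 7 − 1
- noncentrality λ = f² × N
- power = P(F′(u, v, λ) > F₀.₉₅(u, v))

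**Attempt to reproduce the 96% with two groups of 20.** N = 40, u = 1, v = 40 − 1 − 7 − 1 = 31, λ = 0.08 × 40 = 3.2, critical F = 4.16. Power = 41.1%. Without the 7 covariates (v = 38) it is 41.4%, so the covariate count does not explain the gap. A normal approximation for two means gives 43.2%. The 96% is not reproduced.

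**More groups, each of 20:**

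| Groups | N | u | v | λ | Power |
|---|---|---|---|---|---|
| 2 | 40 | 1 | 31 | 3.2 | 41.1% |
| 3 | 60 | 2 | 50 | 4.8 | 46.2% |
| 4 | 80 | 3 | 69 | 6.4 | 52.2% |
| 5 | 100 | 4 | 88 | 8.0 | 57.8% |
| 6 | 120 | 5 | 107 | 9.6 | 63.0% |
| 7 | 140 | 6 | 126 | 11.2 | 67.7% |
| 8 | 160 | 7 | 145 | 12.8 | 71.9% |

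At 20 per group, 96% is first reached with 21 groups (N = 420).

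**The cohorts the protocol names:**

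| Comparison | N | u | Power |
|---|---|---|---|
| 40 PD vs 20 HC | 60 | 1 | 57.5% |
| PD / HC / MSA / dementia (40/20/20/20) | 100 | 3 | 63.3% |
| PD / other synucleinopathy / HC | 100 | 2 | 70.2% |
| Any 1-df contrast over Aim 1.1 | 100 | 1 | 79.9% |
| Six categories, adding 20 spouses and 20 relatives | 140 | 5 | 71.3% |
| PD vs everyone else, same set | 140 | 1 | 91.3% |

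The last two rows assume 40 + 20 + 20 + 20 + 20 + 20 = 140, which the protocol does not state.

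**What 96% would need.** At f² = 0.08 with 7 covariates, the smallest total N is 175, 207, 231, 250 and 266 for u = 1 to 5.

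**What the planned sizes can detect (f²):**

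| Comparison | 80% power | 96% power |
|---|---|---|
| 20 vs 20 | 0.21 | 0.37 |
| 40 PD vs 20 HC | 0.14 | 0.24 |
| Four Aim 1.1 categories, N = 100 | 0.11 | 0.19 |

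**The case against.** Three arguments can be made for the sentence or against the weight given to it.

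*The effect may be mislabelled.* The wording about an effect attributed to category after adjustment also fits an increment in R². If 0.08 is that increment, then f² = 0.08 / (1 − R² of covariates − 0.08), and power depends on a covariate R² that the protocol does not give. Taking that R² as 0, 0.5 and 0.7, 20 versus 20 has 44%, 76% and 96% power; the four Aim 1.1 categories at N = 100 have 67% at 0 and 96% at 0.5. The 96% could therefore be a correct answer for another quantity. That would still be an error, because the text prints f², but it would call for a different correction. The authors must settle the metric before a new figure is printed.

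*Pooling gets close.* Aim 1.2 describes the PD patients who bring relatives as newly recruited, so the total may be nearer 160 than 140; a 1-df contrast then has 94.5%. The 20 is also a minimum: 25 patient, spouse and relative sets added to the 100 of Aim 1.1 make 100 + 75 = 175 and about 96%. The count of 140 is thus uncertain. But these contrasts put unaffected relatives into a two-category test on the whole sample, which is not 20 donors per group.

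*There is other support for the sample size.* The Aim 1 pitfalls section says n = 40 proved adequate in the team's earlier work and that more samples can be collected, and Aim 1 is observational. This bears on whether the study is worthwhile. It supplies no calculation behind the 96%.

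**Conclusion.** The stated power is wrong as written. With the printed f², alpha and 7 covariates, power is 41% for 20 versus 20 and 46% to 72% for three to eight groups of 20. It is 57.5% for 40 PD versus 20 HC and 63% for the four Aim 1.1 categories. Against the claimed 96%, the shortfall on the last two is about 38 and 33 percentage points, and on 20 versus 20 it is 55. The type II error at the stated effect is 59% (20 versus 20), 42% (40 versus 20) or 37% (four categories), not 4%.

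This rests on reading 0.08 as f², as printed, and on λ = f² × N. The unstated number of categories does not rescue the claim. Where the 96% came from cannot be determined from the protocol. The N = 140 figures rest on an assumed count, and the conclusion does not need them.

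**What to change.** Keep the enrolment and rewrite the one sentence.

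1. Name the comparison it refers to, with the number of categories, total N and numerator df.
2. State the effect metric. If 0.08 is confirmed as f², replace the 96% with the line that matches:
   - 20 versus 20: 41% power at f² = 0.08; detectable f² about 0.21 (80% power) and 0.37 (96%).
   - 40 PD versus 20 HC: 57.5%; about 0.14 and 0.24.
   - Four Aim 1.1 categories, N = 100: 63%; about 0.11 and 0.19.

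   If 0.08 proves to be an R² increment, say so, give the assumed covariate R² and its basis, and recompute; the figures above would not then apply.
3. With f² confirmed, stop describing the effect detectable at 96% power as small.
4. Do not interpret non-significant Aim 1 comparisons, in particular PD against MSA or dementia, as if the type II error at that effect were 4%.

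The cost is a sentence and a less favourable power figure. No further subjects or samples are needed.
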